7.3. Placebo study treatment

A corresponding placebo solution is available with excipients matching the

emodepside treatment, but lacking the active pharmaceutical ingredient.

7.4. IMP supply and handling

Formulation and Supplier:

Emodepside will be supplied by the Sponsor, DNDi, as emodepside LSF solution and matching placebo solution.

The study drug will be delivered by the Sponsor to the study site in bulk. It will be the responsibility of a relevant member of the pharmacy/pharmacy delegate to prepare the individual treatments.

Preparation and Dispensing:

Emodepside LSF solution will be dispensed in the Phase 1 Unit to the individual dosing containers by 2 appropriately qualified, unblinded members of the pharmacy team. Instructions provided in the Pharmacy Manual/Study Procedures Manual must also be followed.

7.5. Dose escalation

During the study, the dose will be increased only if the safety, tolerability and PK of the previous dose are acceptable.

Dose escalation will be decided by the Safety Review Group (SRG) at the Safety Review Meeting (see Section 11). The dose will not be escalated until the SRG have reviewed the safety, tolerability and PK data until 48 h after the final dose of study medication in at least 4 subjects on active treatment (ie. at least 6 subjects overall) and agree that it is appropriate to give a higher dose; that decision will be taken in the Safety Review Meeting, before dosing of the subsequent cohort. The next planned dose level may be reduced, a dose level may be re-tested, or an intermediate dose level selected, based on the emerging data.

The dose level will not exceed 20 mg LSF oral solution (1 mg/mL) per day.

7.6. Study stopping criteria

7.6.1. Dose escalation stopping criteria

A dose level will not be repeated, or exceeded, if the results of safety tests give the Sponsor or Investigator cause for concern, or if one of the following dose escalation stopping criteria is met:

- any of the trial stopping criteria in Section 7.6.2 are met.
- the Investigator considers the dose level to be not well tolerated.
- predicted mean plasma concentrations in the subjects at the next scheduled dose level exceed or equal:

- C_{max} : 612 µg/L

- (based on the highest dose in the Single-Ascending Dose (SAD) study: DNDI-EMO-001)

If a cohort fulfils a dose escalation stopping criterion, that dose level will not be repeated.

The scheduled dose of emodepside may be reduced if, for example, the results of safety tests give any cause for concern, or tolerability is poor.

If AEs occur that cause mild or moderate discomfort but do not in any way threaten the health of the subject, that dose level may be repeated, with the aim of further exploring the relationship between dose and AE. If, in the judgement of the SRG, it would not be reasonable to expose more subjects to the level of discomfort experienced by those who have already received the dose, the next scheduled dose may be reduced. The reduction may be either to one of the dose levels that has already been given, or to an intermediate level that has not previously been given; in either case, the aim is to learn more about the relationship between AE and dose (or plasma concentration) of drug.

7.6.2. Trial stopping criteria

The trial will be stopped if either of the following occurs:

- one or more serious AE that is considered to be related to emodepside; or
- 2 or more subjects with a severe or clinically significant AE, considered to be related to emodepside, that occurs in the same treatment group

If, after an internal safety review, it is appropriate to restart the trial, a substantial amendment will be submitted to the MHRA and REC. The trial will not restart until the amendment has been approved by the MHRA and REC.

7.7. Study treatment labelling, packaging

Emodepside supplied by the Sponsor will be manufactured, packed, labelled and shipped according to the current GMP guidelines and local legal rules. Bulk-supplies of emodepside will be delivered to the pharmacy of the Phase 1 Unit.

7.8. Accountability

All study treatments must be kept in a locked room that can be accessed only by the pharmacist or the Investigator. The study treatments must not be used for other purposes other than this protocol. Under no circumstances the Investigator or site staff may supply study treatments to other Investigators or sites, or allow the medications to be used other than as directed by this protocol without prior written authorization from DNDi. Adequate records on receipt, use, return, loss, or other disposition of treatments must be maintained.

Upon receipt of the study drugs, the Investigator or a relevant member of the pharmacy/pharmacy delegate, will send the Sponsor the corresponding acknowledgement of receipt form. This form must be filled (including the date of receipt) and signed by a relevant member of the pharmacy/pharmacy delegate, or the Investigator. An audit trail of all medication transported and dispensed during the study will be maintained.

All investigational materials (medication and packaging) unused in the study will be destroyed by HMR (with the Sponsor's approval), or returned to the Sponsor before or at the termination of the study, together with an accountability form documenting:

- all administered units;

- all unused treatments;
- all units returned after completion of the study, and the date of return.

The study drug will be dispensed only under the restricted conditions defined in the present protocol and the Pharmacy Manual/Study Procedures Manual. Drug will be administered by the Investigator only or his/her delegate.

Time of administration and initials of the person administering the study medication will be documented in the Case Report Form (CRF).

7.9. Storage

Emodepside oral solutions (active and placebo) should be stored at 2–8°C in the original container (upright storage).

7.10. Blinding and procedures for unblinding

The study drug and matching placebo will be identical in appearance in order to preserve the single blind with respect to the subject; the subjects are blinded and will not know which treatment (active or placebo) they are given. The Investigator (including clinical, statistics and data management personnel) and the Sponsor (including the study monitor) will remain blinded during each cohort, so as not to potentially introduce bias, unless safety concerns necessitate unblinding (if the knowledge of the treatment administered is useful for the best medical care of an AE). Investigator pharmacy staff, who'll dispense the IMP, will not be blinded at any time.

For safety and dose escalation purposes, the data may be unblinded at the end of each cohort for review by the SRG. Optionally, a separate, unblinded monitor may be used to check drug accountability monitoring during the conduct of the study, following procedures to avoid unblinding other study personnel.

A sealed copy of the randomisation code will be kept in a locked file in the HMR Pharmacy. A copy will also be kept by the Sponsor. The Investigator will be supplied with sealed envelopes, each one containing the treatment allocation for the subject whose number appears on the outside of the envelope. Those envelopes will be kept in the trial master file, readily accessible to clinical staff. Emergency procedures for revealing medication codes are specified later in this section.

If required, as described in Section 11, advisor(s) independent from the study team may be appointed to review unblinded data to assist decision-making during Safety Review Meetings.

When the database is locked at the end of cohorts 1 and 2 and again at the end of cohort 3, the HMR statistician will inform the Sponsor of his or her intention to break the randomisation code for the finished cohorts. The statistician will break the code, and do the statistical analysis of those data.

If unblinding is required in the interest of the safety of a subject, an Investigator will discuss the matter with the Sponsor before opening the individual code-break envelope for that subject. In a medical emergency, the Principal Investigator or delegate may open the individual code-break envelope for that subject without prior consultation with the Sponsor. In that event, the principal Investigator or delegate will

notify the Sponsor as soon as possible that the randomisation code has been broken for the subject.

When the randomisation code is broken, the reason will be fully documented and entered in source documents and the CRF.

7.11. Concomitant treatments

Prior therapy as indicated in the exclusion criteria (Section 4.2) will not be permitted. The only exception is acetaminophen (paracetamol), which may be taken up to the first dose of trial medication.

No medications (with the exception of acetaminophen (paracetamol) up to 2000 mg per day), will be allowed while the subject is participating in the study, except those medically indicated for the treatment of AEs. If any medication is required, the subject may be withdrawn from the study drug at the discretion of the Investigator and the Sponsor, if use of that medication could compromise the safety of the subject or the scientific value of the trial, and will be followed up until the end of the study. No dietary supplements or herbal remedies that are known to interfere with the CYP3A4 and/or P-gp metabolic pathways will be allowed while the subject is participating in the study, except those medically indicated for the treatment of AEs. Further questions about concomitant medication can be directed to the Sponsor's Medical Expert.

Use of any concomitant medication will be recorded until the last long-term follow-up visit in the source data and CRF with the following information:

- Reason for treatment;
- Name of the drug, type of formulation, and unit strength;
- Dose administered;
- Time and duration of treatment.

Medications taken within 28 days before the first dose of study medication will be documented as a prior medication. Medications taken after the first dose of study medication will be documented as concomitant medications.

8. Study Assessments

8.1. Subject Information and Consent Form

Before any procedures are conducted, the Investigator (or an appropriate delegate at the Investigator site) will obtain written informed consent from each subject in accordance with the procedures described in Section 15.1 on the Subject Information and Consent Form (ICF).

8.2. Timing of Assessments

All procedures will be conducted according the Schedule of events, in Section 5.

General order of assessments

For the study periods described below, when multiple procedures are scheduled at the same time point(s) relative to dosing, the following chronology of events should

be adhered to, where possible:

- Neurological examination and physical examination
- 12-lead ECGs: after 10 minutes rest in the supine position single readings, with the exception of one triplicate reading
- Blood pressure/heart rate: after 10 minutes rest in the supine position
- AE monitoring (spontaneous and solicited AE monitoring will include specific questioning for tolerability and safety)
- PK blood sampling (taken at, or closest to, the nominal time point)
- PK blood sampling for metabolites
- Blood sampling for profiles of glucose, insulin, glucagon, and cortisol; single samples for prolactin and leptin; Laboratory safety blood samples. Urine samples will be collected when possible (dependent on the subject) but within the allowed deviation times.

Every effort should be made to ensure that protocol-required tests and procedures are completed as described. However, it is anticipated that from time to time there may be circumstances outside the control of the Investigator that may make it unfeasible to perform the test. In those cases, the Investigator must take all steps necessary to ensure the safety and well-being of the subject. When a protocol required test cannot be performed, the Investigator will document the reason for the missed test and any corrective and preventative actions which s/he has taken to ensure that required processes are adhered to as soon as possible. The Sponsor study team must be informed of these incidents in a timely manner. Allowable deviations for study assessments are detailed in Section 8.4 of this protocol.

To minimise variability, throughout the study, study staff should also ensure a minimum 10-minute supine period, where possible, before drawing any blood samples (including lab safety assessments).

Throughout the study (from subject signature of the ICF) AEs and concomitant medication will be documented as they are reported by the subjects. Subjects will also be questioned about AEs at the times that blood samples are taken, at follow-up, at long-term follow-up, and at the specific time points detailed in the Schedule of events (Section 5).

8.3. Study visits

Baseline will be considered as the last assessment performed prior to randomisation.

8.3.1. Screening Visit 1

All subjects will be screened within the 28 days before administration of the study medication to confirm that they meet the subject selection criteria for the study. Subjects who fail screening by not meeting the inclusion and/or exclusion criteria may be rescreened at the Investigator's discretion.

Subjects will attend the ward, having fasted overnight for at least 10 h.

The following assessments will be done in order to collect historical safety data, and to assess eligibility for the study:

- Review of inclusion and exclusion criteria
- Complete medical history: including demographic data, previous and concomitant medications (ie, prescription medicine taken within 28 days, or non-prescription drugs and dietary supplements taken within 7 days, before the planned first dose, and/or plan to continue taking throughout the study)
- Full physical examination: see Section 8.5.3. A detailed description of the physical examination will be included in the Study Procedures Manual
- Full neurological examination: see Section 8.5.3. Also a detailed description of the neurological examination will be included in the Study Procedures Manual. Subjects will be given the Ishihara colour perception eye test.
- Body weight and height, vital signs (oral temperature, blood pressure and heart rate will be determined; see Section 8.5.2)
- 12-lead ECGs
- AE monitoring (spontaneous and solicited AE monitoring will include specific questioning for tolerability and safety)
- Urinary drugs of abuse screen (opiates, amphetamines, barbiturates, cannabis, benzodiazepines and cocaine-metabolites) and breath test for alcohol
- Blood sampling for serology (HIV and hepatitis) and for Hb1Ac
- Blood sampling for clinical safety laboratory evaluations:
 - Haematology and coagulation: haemoglobin, haematocrit, MCV, MCH, MCHC, platelets, reticulocytes, white blood cells (WBC) with differential, red blood cells (RBC), HbA1C, activated partial thromboplastin time (aPTT), prothrombin time (PT);
 - Biochemistry: aspartate aminotransferase (AST), alanine aminotransferase (ALT), alkaline phosphatase (AP), glutamate dehydrogenase (GLDH), gamma-glutamyl transpeptidase (GGT), lactate dehydrogenase (LDH), creatinine kinase (CK), amylase, lipase, T4 (free), T3 (free), thyroid-stimulating hormone (TSH), glucose, cholesterol (HDL, LDL, total), triglycerides, creatinine, urea, uric acid, bilirubin (total and conjugated), total protein, sodium, potassium, calcium, chloride and magnesium in serum
 - Leptin and prolactin
- Urinalysis for clinical laboratory safety evaluations, via dipstick test: glucose, ketone bodies, specific gravity, occult blood, pH, proteins, leucocytes, bilirubin, urobilinogen, nitrites

All biological assessments will be performed in fasting state (at least 9 h), and with a 10 minute supine rest before sampling.

To prepare for study participation, subjects will be instructed on the use of the Dietary and Lifestyle Guidelines of the Phase 1 unit and for this study, and will be scheduled to report to the ophthalmology clinic for Screening Visit 2.

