In vitro studies showed moderate plasma protein binding of emodepside in all tested species, with similar values in mice, dogs and humans (fraction unbound of 1.0–1.6 %). In rats, gerbils and rabbits the fraction unbound was slightly higher (2.7–3.1 %). The relevant Phase 1 biotransformation pathway of emodepside in humans, as well as in animal species, was oxidation, with no significant species differences in terms of metabolic pathways. In humans, oxidative metabolism of emodepside was predominantly catalyzed by CYP3A4. The hydrolysis of the ester bonds was observed as an additional metabolic clearance pathway. Transport studies revealed a high permeability of Caco2-cells to emodepside as well as active efflux, which was characterized as being P-glycoprotein mediated. Therefore, a role for P-glycoprotein in the pharmacokinetics of the compound cannot be excluded.

Single dose PK of emodepside was studied in rats, and dogs after single intravenous (i.v.) and oral (p.o.) administration. The absolute bioavailability of emodepside was moderate in rats and dogs with 44 % and 52 %, respectively. Plasma clearance was low in rats (0.77 L/[kg·h]), and dogs (0.30 L/[kg·h]). The volume of distribution was high in both species with 8.5 in dogs and 38.7 l/kg in rats. The plasma elimination half-life was 33 to 43 h in rats and 42 to 35 h in dogs after p.o. and i.v. administration, respectively.

Biodistribution studies with ¹⁴C-labeled emodepside in rats, revealed a moderate to high affinity to most tissues and organs after p.o. administration (1 or 15 mg/kg) with higher concentrations in tissues than in the blood. The highest proportion of emodepside was found in brown and white adipose tissue, the liver and adrenals. There was also a low penetration of the blood-brain barrier. The distribution patterns were similar in both sexes.

The main excretion pathway after oral administration in rats was the faecal/biliary route (about 50 % within 24 h, 83–93 % within 168 h), with only 2–3 % of the dose being found in urine. The unchanged compound emodepside accounted with 45–56 % for most of the dose excreted into faeces. The major metabolites in faeces were identified as the hydrolysis product, its dehydrated and oxidized derivatives as well as three oxidized metabolites.

After repeated oral dosing of ¹⁴C labelled emodepside in rats, the parent compound was the major component found in rat plasma with a small amount of metabolite M1 detected in rat plasma.

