 16. Use of dietary supplements or herbal remedies (such as St John's Wort) that are known to be inducers or inhibitors of CYP3A4, or other co-medications known to be relevant substrates of CYP3A4, during the 28 days before the first dose of study medication (see list in the Study Procedures Manual)
 17. Use of dietary supplements or herbal remedies (such as St John's Wort) that are known to be strong inhibitors of P-gp, or other co-medications known to be relevant substrates of P-gp, during the 28 days before the first dose of study medication (see list in the Study Procedures Manual)
 18. Relevant pathological abnormalities in the ECG at screening, such as:
 - second or third-degree atrioventricular (AV) block; or
 - prolongation of the QRS complex > 120 msec; or
 - QTc-interval (QTcB or QTcF) > 450 msec.
 19. Evidence of drug abuse (via urine testing) at the screening assessment or admission to the ward
 20. Use of excluded therapies that may impact on the interpretation of study results in the opinion of the Investigator or Sponsor
 21. Objection by General Practitioner (GP) to subject entering trial
 22. History of residing for 6 or more continuous months during the last 3 years in regions with endemic parasitic infections, as determined by the Investigator
 23. Possibility that subject will not cooperate with the requirements of the protocol
 24. Wearing of contact lenses during the 1 month before the first dose of study medication. Contact lens wear is not permitted during the study
 25. Presence of an ocular disorder for which topical ocular therapy is currently or

chronically prescribed, including inflammatory eye disease (dry eye allergic conjunctivitis [seasonal allergic conjunctivitis, vernal keratoconjunctivitis, atopic keratoconjunctivitis], uveitis and glaucoma)

26. History of ocular disease requiring ongoing treatment
27. Past ocular surgery, including laser or other refractive corneal surgery
28. Evidence of eye irritation, visual difficulties, corneal opacity, ocular surface (corneal or conjunctival damage, with or without ocular symptoms)
29. Evidence of narrow anterior chamber angles causing increased risk of acute glaucoma
30. Evidence of ocular media opacity including lens opacity/vitreous opacities
31. Evidence of retinal or optic nerve pathology
32. Evidence of pronounced colour blindness, as indicated by an Ishihara score of 9/13 or below

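### Exclusions 16 and 17 look back 28 days, but the screening history asks about supplements and non-prescription drugs for 7 days only, and for co-medications both exclusions name only substrates

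*Protocol*

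**What the plan says.** **Eligibility rule.** In Protocol 4.2, exclusion 16 covers supplements and herbal remedies "that are known to be inducers or inhibitors of CYP3A4", and then adds "or other co-medications known to be relevant substrates of CYP3A4, during the 28 days before the first dose of study medication". Exclusion 17 has the same structure for P-gp: supplements and herbals "known to be strong inhibitors of P-gp, or other co-medications known to be relevant substrates of P-gp, during the 28 days" before the first dose. Synopsis criteria 24 and 25 match. Exclusion 15 bars any prescription medicine for 28 days and any over-the-counter medicine except paracetamol for 7 days. Exclusion 20 lets the investigator or sponsor exclude at discretion.

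**What is collected.** The Screening Visit 1 history (Protocol 8.3.1) asks for "prescription medicine taken within 28 days, or non-prescription drugs and dietary supplements taken within 7 days, before the planned first dose", and for products the subject plans to go on taking. Section 7.11 gives a different window: "Medications taken within 28 days before the first dose of study medication will be documented as a prior medication". It does not name supplements or herbals in that sentence. Admission on Day -3 (8.3.3) lists a urinary drug screen, an alcohol breath test and adverse event monitoring, with no medication question.

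**Why these pathways matter.** Section 1.3 states: "In humans, oxidative metabolism of emodepside was predominantly catalyzed by CYP3A4". It also reports P-gp-mediated efflux and says that a role for P-gp in the pharmacokinetics cannot be ruled out.

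**The concern.** The one supplement look-back that the protocol specifies is shorter than the exclusion it has to support. A volunteer who stopped St John's Wort 10 days before dosing breaches exclusion 16, yet a history taken as written would not record it.

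The second difficulty is the class of drug. If emodepside is cleared by CYP3A4 and carried by P-gp, the agents expected to alter its exposure are inhibitors and inducers. For co-medications both exclusions name substrates instead.

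Pharmacokinetics is a secondary objective with six active subjects per cohort, and an escalation review may proceed on four. An undetected subject with altered exposure would carry real weight in those summaries.

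**Working it through.** The plan states no figure to reproduce, so the check sets the windows and drug classes side by side.

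**1. Look-back windows, counted back from first dose on Day 0**
- Supplements and herbals, eligibility (exclusions 16 and 17): 28 days, Days -28 to -1.
- Supplements and non-prescription drugs, history (8.3.1): 7 days, Days -7 to -1, plus planned continuing use.
- Medications, recording (7.11): 28 days, with no split by type.
- Gap between rule and history: 28 - 7 = 21 days, Days -28 to -8.

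**2. Timing of the question.** Visit 1 may fall on Day -28 to Day -3. The 7 days are counted from the planned dose, so for anyone seen on Days -28 to -8 they have not started, and the item can pick up only planned use. Lengthening the window alone would not close this: a 28-day question asked on Day -20 covers only Days -28 to -20. A repeat on Day -3 is needed to cover the rest up to admission.

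**3. What the substrate wording leaves open**
- Prescription inhibitor or inducer within 28 days: barred by exclusion 15.
- Over-the-counter inhibitor or inducer within 7 days: barred by exclusion 15 (paracetamol excepted).
- Supplement or herbal inducing or inhibiting CYP3A4, or strongly inhibiting P-gp, within 28 days: barred by 16 or 17.
- Non-prescription co-medicine that inhibits or induces, is not a substrate, and was last used 8 to 28 days before dosing: no named criterion applies.

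**4. Downstream detection.** SAP 13.2 treats breaches of entry criteria as major deviations, found by reviewing data listings. Use that was never collected cannot appear there. The two PK populations (SAP 9) have no condition that would remove such a subject.

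**5. Illustrative size.** Assume that one active subject's exposure is halved or doubled and the others are equal.
- One of six, geometric mean: 0.5^(1/6) = 0.891 (-11%); 2^(1/6) = 1.122 (+12%).
- One of six, arithmetic mean: (5 + 0.5)/6 = 0.917 (-8%); (5 + 2)/6 = 1.167 (+17%).
- One of four, geometric mean: 0.5^(1/4) = 0.841 (-16%); 2^(1/4) = 1.189 (+19%).

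If the effect has worn off by Day 0, the shift is zero. The documents give no interaction size or offset time, so they do not say where in this range a real case would fall.

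**The case against.** The strongest reply is that the eligibility rule itself is intact. The same screening visit includes a review of all the criteria, Table 2 repeats that review on Day 0, and 8.3.6 requires eligibility to be settled before randomisation. Section 7.11 opens by disallowing prior therapy named in 4.2, and 8.2 has concomitant medication documented as subjects report it. This stands. A reader might infer that subjects with altered exposure may enter under the rules, or that most of the 28 days is never enquired into. The documents do not support either for supplements: such a user stays ineligible, and the criteria review may elicit the use. What remains is that this review depends on what the subject is asked, and the only look-back written down for supplements is 7 days.

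On drug class, exclusion 15 removes all prescription medicines, exclusion 20 is a discretionary backstop, and both exclusions refer to a Study Procedures Manual list that is not among the documents. That list may already name inhibitors and inducers. The gap is therefore narrow, and the documents identify no product that falls in it.

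A reader might also infer that a missed subject could change the outcome of the 612 µg/L stopping rule. That is not shown. Section 1.4 gives a mean Cmax of 612 ng/mL at 40 mg and rough dose proportionality, so a first 10 mg dose scales to 612 × 10/40 = 153 ng/mL before accumulation. A shift of about 11% in one cohort mean is small against that distance, and escalation also rests on safety and tolerability.

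**Conclusion.** The point holds as a mismatch between an exclusion and the data collected to verify it. For supplements and herbals, disqualifying use on Days -28 to -8 could go undetected, and would then also be missing from the SAP's deviation review. For co-medications, the substrate wording does not match the rationale in Section 1.3, but it leaves open only non-prescription inhibitors or inducers last used 8 to 28 days before dosing.

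The 21-day gap follows directly from the text. The shift of -11% or +12% in a cohort geometric mean rests on an assumed halving or doubling in one of six subjects and is illustrative. No dose decision is shown to change. The correction is worth making because it costs little and protects small-sample PK summaries; it does not call the design into question.

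**What to change.** - In Protocol 8.3.1, set the history look-back for non-prescription drugs, dietary supplements and herbal remedies to the 28 days that exclusions 16 and 17 already use, and make 7.11 name supplements and herbals so that the two sections agree.
- In 8.3.3, repeat the question at admission on Day -3, and record the answer in the CRF so that a breach can reach the SAP deviation listing.
- Reconcile the synopsis, 4.2 (exclusions 15 to 17), 7.11 and 8.3.1 on which class of co-medication exclusions 16 and 17 are meant to cover: substrates, or inhibitors and inducers. Check the Study Procedures Manual list against the answer. Which washout rule applies is for the sponsor and investigator to decide.

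The cost is some wording, one CRF question and possibly a few more screen failures. No procedure is added.
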